5.0 RESEARCH DESIGN AND METHODS

5.1 Collaborating sites

There are no collaborating sites. Patients will be identified from the general surgery clinics at UWHC, the UW DHC, The American Center (TAC), and UW East Clinic. All patients enrolled in the study will undergo surgery at, and be admitted to, UWHC.

5.2 Data extraction from medical record

The following information will be extracted from the subject's medical record at the time of preoperative visit, following enrollment in the study: date of birth, age, gender, race, height, weight, information about planned surgery, co-morbidities, past medical history, past surgical history, current medications, allergies, and smoking history. Additional data extracted from the subject's medical record following their operation includes: operation performed, length of operation (minutes), type of anesthesia (general, regional, MAC, local), volume of intravenous fluids administered intra-operatively, estimated blood loss, placement of epidural, type of anesthetic medications used, placement/removal of IUC in the operating room, volume of urine output in the operating room, and whether or not straight catheterization was performed at the conclusion of the case in the operating room.

Data to be extracted from the medical record following discharge from the hospital includes: hospital length of stay (days), whether or not the subject was discharged with an indwelling catheter, diagnosis of urinary tract infection within 30 days of operation, and urine culture data if applicable.

All of the data extracted from a subject's medical record will be entered into the ICTR OnCore Clinical Research Management System.

5.3 Data collection

At the time of the pre-operative visit, following enrollment in the study, subjects will fill out the International Prostate Symptom Score (IPSS) Survey. This survey is a validated, selfadministered 7-item questionnaire that assesses obstructive lower urinary tract symptoms. Additionally, subjects will be administered a questionnaire that asks about history of prior problems with urinary retention and prior urinary tract surgeries or procedures, consisting of a total of 3 questions. Subjects may decline to answer the survey questions on the IPSS survey, but this will result in ineligibility for the trial, as IPSS score is a stratification variable for randomization. Subjects may skip the urinary tract surgery/history questions if they feel uncomfortable or embarrassed, and this will not result in exclusion from the study. Case report forms (CRFs) will be utilized to collect data prospectively during the subject's postoperative course while inpatient. This data will be collected by a study team member, and will include time of arrival and departure from the operating room, time of first void, date/time of IUC removal, date/time of first void after catheter removal, first post-void residual volume, date/time of first straight catheterization (if applicable), date/time of all subsequent straight catheterizations (if applicable), date/time of IUC replacement (if applicable), and date/time of the first two adequate voids (if applicable). Finally, subjects will be contacted by telephone 30-

40 days after the date of surgery to ask if they have been treated for a urinary tract infection since discharge from the hospital (in order to capture UTIs that are diagnosed outside of our hospital system). Additionally, data regarding adverse events will be collected using an Adverse Event Log. A study team member will make contact with the subject at two separate time points to inquire about adverse events: 1) on the day of surgery (in person, in the hospital), and 2) postoperatively via telephone call 30-40 days after surgery. Additionally, adverse events will be abstracted from the electronic medical record during the immediate postoperative period. AEs occurring following surgery up until 48 hours after discontinuing study drug will be abstracted from the subject's EMR.

5.4 Confidentiality protections, sharing of data, disposition of data

Subjects enrolled in the study will be sequentially assigned a unique 3-digit study identification number, which will be used to identify the subject throughout the course of the study. The link between the subject's identifiers (i.e. name, MRN, birthdate) and the subject ID will be available in the OnCore system. All data exported from the system will only contain the Subject ID number, and will not contain other subject identifiers.

All paper forms containing subject information or data will be kept locked in the offices of the PI or study coordinator.

5.4.1 ICTR OnCore Clinical Research Management System

This study will utilize the clinical research management software, Online Collaborative Research Environment (OnCore), adopted by the School of Medicine and Public Health (SMPH) and available to all researchers conducting clinical research studies. The instance of OnCore that will be utilized for this study is supported and managed by the UW Institute for Clinical and Translational Research (ICTR). OnCore-CRM has been, and continues to be deployed nationally at multiple academic medical centers, some of which are NIH Clinical and Translational Science Award (CTSA) sites including UW ICTR, and is an extension of technology currently used in more than two dozen Cancer Centers around the country.

ICTR OnCore is a sophisticated, web-based data management system that: a) ensures secure, easy data entry at multiple sites; b) integrates multiple data sources such as individual studies and patient registries; c) provides controlled, secure access to sensitive data using role-based access control; d) provides workflow automation; and e) allows export and reporting of data for Data and Safety Monitoring Boards and biostatisticians.

This software provides protocol management functions (e.g. subject scheduling; screening, data organization), maintains updated forms, addresses budget development, billing, and fiscal management, generates summary reports, and provides essential links with other research administration and electronic medical records systems. ICTR OnCore eases the burden of the individual researcher and unifies protocol management within research programs and including researchers at multiple sites, enhancing protocol integrity and regulatory compliance efforts.

> Current Status: Both UW ICTR and SMPH are committed to the use of ICTR OnCore on an enterprise-wide scale. ICTR OnCore completed the initial pilot phase in 2009 and has been fully implemented for all clinical research groups across the infrastructure. Many workflows and processes have been identified and standardized within ICTR OnCore for use across the spectrum.

ICTR OnCore-CRM is hosted by the UW School of Medicine and Public Health (SMPH) Information Technology (IT) Office on its server farm with redundant systems at two, environments are maintained for production, training, and testing. The application-programming model employed in ICTR OnCore-CRM conforms to the Java 2 Platform, Enterprise Edition (J2EE) standard for web-based applications. J2EE is a widely accepted standard for developing multi-tier enterprise applications and is based on standardized, modular components. The J2EE standard includes compliance tests to ensure portability of applications. In addition to portability, J2EE provides a JDBC API for database access and a proven security model that is applicable to Internet applications. J2EE also supports Enterprise JavaBeans components, Java Servlets API, JavaServer Pages, and XML technology. The ICTR OnCore-CRM application uses these, Apache Web services, and an application server (JBoss/TomCat). The backend is an Oracle® relational database management system maintained by SMPH IT. Both the database and application servers are behind a firewall maintained by SMPH IT staff. Several complete environments are maintained for production, training, testing, and validation. This provides for a high level of system security and reliability.

The data collected during the course of the study will be stored in OnCore. However, as is necessary for the completion of remote data analysis and travel to/from conferences where data may be presented, data exported from OnCore may be transferred to a limited number of password-protected and encrypted laptops belonging to study staff as necessary. In this case, data would be stored on a password protected and encrypted USB drive in order to transfer data to the laptop. Laptops and USB drives will only contain data that has been exported from OnCore and containing only Subject ID number without associated subject identifiers. Only study staff will have access to such USB drives and laptops. Laptops and USB drives will not contain the key to the code.

The clinical research pharmacy will maintain the randomization code sheet, and this will not be made accessible to other study team members until completion of the study (or at interim data and safety monitoring analysis). Unblinding at interim data analysis will only occur for subjects whose data collection is complete.

5.5 Sub-studies/correlative studies

The data collected during this study will be used to retrospectively identify risk factors that are associated with urinary retention as described in Specific Aim 2. This analysis will be performed both on the placebo treated group alone and the overall study population. Logistic regression will be used for this analysis. The response variable will be the primary endpoint (need for any

intermittent catheterization). The various preoperative and operative variables collected during the study will be used as predictor variables in this analysis.

5.6 Timeline

5.6.1 Screening for eligibility

Pre-screening of general surgery clinic patients will occur prior to initial contact. If a patient is found to be eligible on pre-screening and upon contact has expressed interest in learning more about the study, then formal screening for eligibility will occur after informed consent is obtained. If the subject is determined to be potentially eligible based on the gross eligibility criteria reviewed during the pre-screening process, the subject will be invited to learn more about the study. If the patient is interested in participating in the study at that time, the enrollment protocol, including obtaining informed consent, will be initiated. If the patient has another scheduled preoperative visit that will occur more than one week prior to their scheduled surgery date, then the informed consent and enrollment procedures may be deferred until the next visit. Likewise, if the patient does not have another preoperative clinic visit appointment scheduled, but would like more time to make a decision about participation in the study, arrangements will be made for future follow up with a study team member as described below.

5.6.2 Consent/Enrollment/Baseline

After the pre-screening procedures determine the subject may be potentially eligible, and the subject has expressed an interest in participating in the study, we will proceed with the informed consent process (either at the initial or subsequent preoperative clinic visit). As part of formal screening for eligibility, all women of childbearing age and potential will be given a pregnancy test. Upon completion of the screening procedures, and determination that the subject is eligible to participate, the individual will be considered enrolled in the study. Due to constraints of the study related to the medication starting 7 days preoperatively, consent and enrollment must be completed at least 7 days prior to the scheduled surgery. If after the initial clinic visit, the patient has another scheduled preoperative clinic visit prior to 7 days preoperatively, then the patient will be given the opportunity to take the consent form home if they so desire, and then signed informed consent will be obtained at the next clinic visit if applicable. If, however, the patient does not have an additional preoperative clinic visit scheduled and needs additional time to consider participation in the study, he or she may bring written materials home and study personnel will follow up via telephone call. If the patient is interested in participating in the study, then a visit will be arranged with the study coordinator (prior to 7 days preoperatively) for the patient to sign the consent form, undergo formal eligibility screening, and complete enrollment.

After enrollment, the subject will fill out the first data collection form, which includes the IPSS survey and questionnaire regarding history of previous urinary retention and urinary tract surgery or procedures. The subject may choose to

decline to answer any of the IPSS survey questions, however, this will result in exclusion from the study, as IPSS score is being used for stratification in the randomization process. Following completion of the IPSS survey, the subject will be randomized by the clinical research pharmacy. The subject will be given a 14-day supply of tamsulosin or placebo, according to randomization, along with instructions for taking the medication.

5.6.3 Treatment period

Treatment will start 7 days prior to scheduled surgery and will continue postoperatively for up to 7 days while the subject is still in the hospital (for a total of 14 doses). A member of the study team will contact the subject via telephone as a reminder on the day that treatment is to be initiated. If a subject discontinues study treatment (chooses to withdraw from the study) prior to their scheduled surgery, the subject will be discontinued and replaced, and reason for withdraw from study will be noted. Data will continued to be collected for these subjects and their data will be included on an intent-to-treat basis, but they will be replaced for sample size. If the subject discontinues study drug any time after their surgery, the subject will be followed with intent to treat and will not be replaced. If a subject's planned surgery is postponed PRIOR to initiation of treatment but is rescheduled to within 30 days of when the subject was randomized, then the subject may stay enrolled in the trial, will keep their same treatment assignment, and will be given a new start date for treatment (7 days before their rescheduled surgery date). If, however, the surgery is postponed or cancelled AFTER initiation of treatment, then the subject will be taken off treatment and discontinued from the study. If the subject has not yet initiated treatment and their surgery is rescheduled to a date that is more than 30 days from the date of randomization, the subject will be discontinued.

Once a subject completes the bladder management protocol (is voiding spontaneously and completely—specifically, 2 consecutive voids with PVR less than 200mL) OR requires replacement of an IUC, the treatment will be discontinued within 24 hours, and the protocol is complete. The protocol may be completed as early as POD#0. The maximum number of days of treatment will be 14 (up until POD#6, i.e. last dose given in the evening of POD#6). No subjects will be discharged from the hospital on study medication.

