4.2 Eligibility Criteria

4.2.1 Inclusion Criteria

Patients must be 18 years of age or older, English-speaking, able to provide informed consent, and scheduled to undergo an elective, complex intra-abdominal operation with a planned postoperative inpatient stay of at least 1 night. Eligible operations will include any of the following operations approached via any operative approach (i.e. open, laparoscopic, hand-assisted laparoscopic, singleincision laparoscopic, or robotic):

- 4.2.1.1 Partial colectomy
- 4.2.1.2 Total abdominal colectomy
- 4.2.1.3 Proctocolectomy
- 4.2.1.4 Low anterior resection
- 4.2.1.5 Abdominoperineal resection
- 4.2.1.6 Restorative proctocolectomy/IPAA
- 4.2.1.7 Proctopexy (transabdominal) for prolapse
- 4.2.1.8 Intestinal stricturoplasty
- 4.2.1.9 Lysis of adhesions
- 4.2.1.10 End or diverting colostomy reversal
- 4.2.1.11 lleostomy reversal
- 4.2.1.12 Closure of enterocutaneous, enteroenteric, or enterocolic fistula
- 4.2.1.13 Partial or complete gastrectomy
- 4.2.1.14 Small bowel resection
- 4.2.1.15 Small bowel diversion/ostomy

Post-Op Urinary Retention Protocol

Version: 5.0, December 8, 2017 Page 6 of 32

- 4.2.1.16 Large bowel diversion/ostomy
- 4.2.1.17 Pancreaticoduodenectomy
- 4.2.1.18 Pancreatectomy
- 4.2.1.19 Hepatectomy
- 4.2.1.20 Gastric bypass
- 4.2.1.21 Sleeve gastrectomy
- 4.2.1.22 Nissen/Dor/Toupet fundoplication
- 4.2.1.23 Transabdominal adrenalectomy
- 4.2.1.24 Splenectomy
- 4.2.1.25 Complex abdominal wall hernia repair (i.e. Rives-Stoppa type repair, large laparoscopic ventral hernia repair)
- 4.2.1.26 Exploratory laparotomy
- 4.2.1.27 Other comparable complex intra-abdominal operations
- 4.2.2 Exclusion Criteria
 - 4.2.2.1 Less than age 18
 - 4.2.2.2 Allergy or contraindication to tamsulosin
 - 4.2.2.3 Serious sulfa allergy
 - 4.2.2.4 Current use of alpha blocker (alfuzosin, doxazosin, prazosin, silodosin, terazosin, verapamil, tamsulosin, phenoxybenzamine) or oral alpha agonist (midodrine)
 - 4.2.2.4.1 Initiation of one of these medications during the intervention phase of the study will result in subject withdrawal from the study.
 - 4.2.2.5 Current warfarin use
 - 4.2.2.6 Pre-existing indwelling urinary catheter, suprapubic catheter, or urostomy
 - 4.2.2.7 End stage renal disease or dialysis-dependence
 - 4.2.2.8 Sitting systolic blood pressure in the upper extremity of less than 100mmHg at time of eligibility screening
 - 4.2.2.9 Presence of orthostatic hypotension at the time of eligibility screening

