9.0 DRUG FORMULATION AND PROCUREMENT

9.1 Tamsulosin hydrochloride (NDC 0597-0058-01)

- 9.1.1 Other names: FLOMAX
- 9.1.2 Classification: alpha_{1A} adrenoceptor antagonist
- 9.1.3 Mode of Action: Tamsulosin works by blocking alpha_{1A} adrenergic receptors in the prostate, prostatic urethra, and bladder neck, which results in relaxation of the smooth muscles in the bladder neck and prostate, thereby reducing bladder outlet obstruction.
- 9.1.4 Storage and stability

Stored at 25 degrees Celsius (77 degrees F); excursions permitted to 15 degrees C to 30 degrees C (59 degrees F to 86 degrees F)

9.1.5 Dose specifics: 0.4mg orally dosed one time per day, 30 minutes after a meal, in the evening

- 9.1.6 Preparation: capsule
- 9.1.7 Route of administration: orally; capsules should not be crushed, chewed, or opened
- 9.1.8 Incompatibilities
 - 9.1.8.1 Other alpha-adrenergic blockers

Per package insert: "The pharmacokinetic and pharmacodynamic interactions between FLOMAX capsules and other alpha-adrenergic blocking agents have not been determined. However, interactions may be expected and FLOMAX capsules should NOT be used in combination with other alpha-adrenergic blocking agents." Patients taking concomitant alpha blockers (including verapamil, which has alpha blockade action at therapeutic doses) will be excluded from the study.

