9.1.8.3 Warfarin

Per package insert: "A definitive drug-drug interaction study between tamsulosin hydrochloride and warfarin was not conducted. Results from limited *in vitro* and *in vivo* studies are inconclusive. Therefore, caution should be exercised with concomitant administration of warfarin and FLOMAX capsules." We will exclude patients taking warfarin.

9.1.8.4 Strong inhibitors of CYP3A4 (boceprevir, clarithromycin, conivaptan, grapefruit juice, indinavir, itraconazole, ketoconazole, lopinavir, nefazodone, nelfinavir, posaconazole, ritonavir, saquinavir, telaprevir, telithromycin, voriconazole) and CYP2D6 (bupropion, fluoxetine, paroxetine, quinidine)

It is recommended that doses higher than 0.4mg daily should not be used in combination with strong inhibitors of CYP3A4 or CYP2D6 and that caution should be exercised when using tamsulosin in combination with such drugs. Studies have demonstrated an increased AUC and C_{max} when tamsulosin is taken in combination with strong inhibitors of CYP2D6 or CYP3A4, but these increases have been shown to still fall equivalently or below the higher U.S. dosage of 0.8mg daily. One study specifically examining clinical effects (i.e. orthostasis) of

concomitant tamsulosin/paroxetine and tamsulosin/ketoconazole found no significant clinical effect of these medications being co-administered. Patients taking strong inhibitors of CYP3A4 or CYP2D6 will not be excluded from the study, however they will be advised about potential increased risk of side effects.

- 9.1.9 Availability: commercially available
- 9.1.10 Side effects (reported in package insert; data derived from two U.S. clinical trials (US92-03A and US93-01)^{7,8}:

	Tamsulosin 0.4mg	Placebo
	(n=502)	(n=493)
Body as whole		
Headache	97 (19.3%)	99 (20.1%)
Infection	45 (9.0%)	37 (7.5%)
Asthenia	39 (7.8%)	27 (5.5%)
Back pain	35 (7.0%)	27 (5.5%)
Chest pain	20 (4.0%)	18 (3.7%)
Nervous System		
Dizziness	75 (14.9%)	50 (10.1%)
Somnolence	15 (3.0%)	8 (1.6%)
Insomnia	12 (2.4%)	3 (0.6%)
Libido decreased	5 (1.0%)	6 (1.2%)
Respiratory System		
Rhinitis	66 (13.1%)	41 (8.3%)
Pharyngitis	29 (5.8%)	23 (4.7%)
Cough increased	17 (3.4%)	12 (2.4%)
Sinusitis	11 (2.2%)	8 (1.6%)
Digestive System		
Diarrhea	31 (6.2%)	22 (4.5%)
Nausea	13 (2.6%)	16 (3.2%)
Tooth disorder	6 (1.2%)	7 (1.4%)
Urogenital System		
Abnormal ejaculation	42 (8.4%)	1 (0.2%)
Special Senses		
Blurred vision	1 (0.2%)	2 (0.4%)

Table reproduced (with modification) from Flomax package insert.

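### No step described between screening and first dose would detect a newly started excluded drug, including when surgery is postponed and the start date is reset

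*Combined protocol and SAP*

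**What the plan says.** **Screening and supply.** Eligibility is determined once, at formal screening after consent (sections 5.6.1, 5.6.2 and 8.0). Section 5.2 lists current medications among the data taken at the preoperative visit; its postoperative and post-discharge lists do not include them again. After randomization the subject takes home a 14-day supply (5.6.2).

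**Start of dosing.** "Treatment will start 7 days prior to scheduled surgery" (5.6.3). Section 5.6.2 requires enrollment at least 7 days before surgery and gives no upper limit.

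**Postponement before treatment.** If surgery "is rescheduled to within 30 days of when the subject was randomized", "then the subject may stay enrolled in the trial". Such subjects "will keep their same treatment assignment, and will be given a new start date for treatment" (5.6.3). A new date more than 30 days after randomization means discontinuation.

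**Contact at first dose.** A team member is to "contact the subject via telephone as a reminder on the day that treatment is to be initiated" (5.6.3). Section 8.0 lists the same contact as a call or a text message.

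**Drug rules.** Under 4.2.2.4.1, which follows the alpha-blocker and midodrine exclusion, "Initiation of one of these medications during the intervention phase of the study will result in subject withdrawal from the study". Section 9.1.8.1 cites the package insert: "FLOMAX capsules should NOT be used in combination with other alpha-adrenergic blocking agents". It adds that patients on such drugs, verapamil included, are excluded. Section 9.1.8.3 states: "We will exclude patients taking warfarin".

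**The concern.** The exclusions exist because of what happens when tamsulosin is taken with another drug, so they matter on the days when capsules are swallowed. The protocol enforces them at a clinic visit that may be weeks earlier. A subject prescribed verapamil, another listed alpha blocker or warfarin in between already holds the capsules and takes them at home. Staff following the written procedures would have no prompt to ask. What is at stake is the safety of those subjects and agreement between the trial's conduct and its own exclusion criteria.

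**Working it through.** The plan gives no figure on this point to reproduce. The check is one subtraction and a comparison of sections.

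**1. Longest interval for a postponed subject.** Inputs, both from 5.6.3: rescheduled surgery at most 30 days after randomization; dosing starts 7 days before surgery.

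Latest first dose = 30 − 7 = 23 days after randomization. Screening precedes randomization or falls on the same day, so the interval from screening is at least as long.

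**2. Interval when surgery is not postponed.** Section 5.6.2 sets a minimum of 7 days and no maximum. As an illustration, surgery booked from the outset for day 60 after randomization would mean a first dose on day 60 − 7 = 53. A subject postponed to day 31 would be discontinued. The 30-day limit therefore does not cap the interval for subjects in general.

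**3. Contacts between screening and the end of preoperative dosing.**

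| Time | Contact | Asks about medications? |
|---|---|---|
| Preoperative visit | Screening, enrollment, randomization, supply of capsules | Yes |
| Postponement, if any | New start date (5.6.3) | Not stated |
| Study day 1 | Reminder (5.6.3; 8.0) | Not stated |
| Study days 1–7 | Self-administration at home, seven doses (7.1; 8.0) | No contact planned |
| Study day 8 | Adverse-event interview (7.2; 8.0; 13.0) | Not stated; all seven doses are already scheduled |

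**4. Does 4.2.2.4.1 close the gap?** Three limits appear when it is read beside 9.1.8.1 and 9.1.8.3.

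- *Drugs.* It covers the drugs in 4.2.2.4. Warfarin is in 4.2.2.5 and has no rule for later initiation.
- *Time.* It applies to a phase the protocol does not define. Section 8.0 uses similar wording for the periods of dosing, which suggests that a drug started before day 1 falls outside it, but the text does not settle this.
- *Detection.* It states a consequence and names no step that would reveal the new drug before the first capsule.

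**5. Number affected.** The documents give no rate. For scale only, assume 0.5% to 2% of all enrolled subjects start an excluded drug in the interval. With the enrollment goal of 294 (10.2): 294 × 0.005 = 1.5 and 294 × 0.02 = 5.9, or about 1 to 6 subjects. Under 1:1 allocation about half, 0.7 to 2.9, would be on tamsulosin. The range is an assumption. The number postponed is also unknown.

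**The case against.** The strongest reply is that the plan is silent on a check but does not order anyone to dose an ineligible subject. Retention after postponement is permissive, sections 9.1.8.1 and 9.1.8.3 exclude patients on these drugs without limiting that to the screening date, and 4.2.2.4.1 shows that later initiation was considered. This stands. A reader might infer that a subject who has since met an exclusion is simply put on study drug; no passage says so.

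Other limits also stand.

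- A reader might treat all the drugs as combinations the protocol forbids outright. The insert's prohibition quoted in 9.1.8.1 concerns alpha blockers. For warfarin, the insert text in 9.1.8.3 calls the evidence inconclusive and advises caution; the exclusion is the protocol's own.
- A reader might extend the point to blood pressure. Criteria 4.2.2.8 and 4.2.2.9 are expressly tied to the time of screening, so applying them once is what the plan intends.
- A reader might claim damage to the intent-to-treat comparison. Section 5.6.3 already keeps subjects who stop before surgery in follow-up and in that analysis, and replaces them for sample size. A subject found before day 1 who never starts would dilute the comparison at least as much as one who stops after some doses. No statistical loss is shown.
- The instructions handed out with the capsules (5.6.2) are not reproduced, and the consent pages are not available. Either might ask subjects to report new medicines.

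None of this supplies the missing step. Permission to stay enrolled carries no stated condition except the 30-day window, and an exclusion that nobody is told to re-ask about cannot be applied.

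**Conclusion.** The point holds as a gap in detection. As far as the available text shows, no step between screening and first dose would reveal a newly started drug listed in 4.2.2.4 or 4.2.2.5. The interval reaches 23 days from randomization after a postponement and has no stated maximum otherwise. Seven more days of home dosing follow before the next contact. The existing withdrawal rule narrows the gap but does not close it.

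The conclusion rests on the written schedule being followed as it stands and on the unseen subject instructions not containing such a check. How many subjects would be affected is unknown and probably few. The benefit of correcting it is subject safety and consistency with the protocol's own exclusions. It is worth doing because it is cheap; it does not call the primary analysis into question.

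**What to change.** 1. In 5.6.3 and 8.0, make the Day 1 contact a telephone call for every subject, placed before that evening's first capsule. Have the caller re-ask about the medications in 4.2.2.4 and 4.2.2.5, look at the medication list in the electronic record, and record the answer. This also removes the difference between the two sections on call versus text.
2. Add the same check to the postponement rule in 5.6.3, before a new start date is given.
3. Reconcile 4.2.2.4, 4.2.2.4.1, 4.2.2.5, 5.6.3, 8.0, 9.1.8.1 and 9.1.8.3. The text should define the intervention phase and state how a subject who meets a drug exclusion after randomization is handled. It should also say whether follow-up continues, whether the subject is replaced, and how withdrawal under 4.2.2.4.1 fits with the intent-to-treat follow-up in 5.6.3. The clinical rule itself is for the sponsor and investigator to decide; none is proposed here.

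Cost: a few more minutes on a contact already scheduled, a brief record check, and loss of the text-message option. Some randomized subjects may be found to meet an exclusion before dosing, so the handling in item 3 needs to be settled first.
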